**Zydus Discovery DMCC** 

- 13. History of malignancy in the past 5 years and/or active neoplasm with the exception of resolved superficial non-melanoma skin cancer.
- 14. History of chronic rejection of liver transplant graft.
- 15. Acute cellular rejection of liver transplant graft within the past 6 months.
- 16. Evidence of Acute cellular rejection (ACR) or chronic rejection (CR) or alternative etiologies to NAFLD must be ruled out within 4-6 weeks prior to enrollment into the study by either a liver biopsy or at the discretion (clinical judgement and according to local standard of care) of the treating hepatologist.
- 17. Any of the following laboratory values:
  - a. White blood cell count  $< 2.5 \times 10^3 / \text{uL}$
  - b. Neutrophil count  $< 1.5 \times 10^3/uL$
  - c. Serum bilirubin >1.5 mg/dL
  - d. Serum ALT >3X ULN
  - e. INR >1.2
  - f. Renal impairment as demonstrated by baseline estimated glomerular filtration rate  $(eGFR) < 60 \text{ mL/min}/1.73\text{m}^2$
  - g. Abnormal screening total creatine kinase
  - h. Abnormal screening lipase or amylase
- 18. Poorly controlled diabetes as defined by an HbA1c >8.5% within the past 6 months.
- 19. Subjects with history of excessive alcohol intake, defined by ≥21 units of alcohol per week in males and ≥14 units of alcohol per week in females for two years prior to enrollment, where a "unit" of alcohol is equivalent to a 12 ounce (oz.) beer, 4 oz. glass of wine, or 1 oz. shot of hard liquor.
- 20. Subject tests positive for a urine drug screen.
- 21. Subject has a history of chronic (uncontrolled) pain.

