**Zydus Discovery DMCC** 

#### **Protocol Deviations:**

Protocol deviations/ will include but are not limited to the following;

- Subjects that did not meet entry criteria but are enrolled into the study.
- Subjects that received the wrong treatment or incorrect dose.
- Subjects that received an excluded medication.
- Subjects that met the discontinuation criteria but continued in the study.
- Failure to report within specified timelines of the planned visits.
- Failure to perform a study procedure/assessment.
- IP non-compliance (<80% or >120%).

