### Discontinuation of patients from the Study Drug

- Discontinue any patient with an AE of Common Terminology Criteria for Adverse Events (CTCAE) grade 3 or higher that is possible or probably drug related and discontinue any patient with an AE of CTCAE grade 4 regardless of attribution to study drug.
- If any of the following criteria are met, the patient shall be immediately discontinued from drug and followed until resolution of adverse events and laboratory values shall be returned to baseline.
  - a. Total bilirubin ≥3.0 mg/dL.
  - b. Total CK >5 X ULN.
  - c. Amylase or lipase >ULN.
  - d. eGFR <60 mL/min/1.73 m^2 and where the value is reconfirmed after 24 hours repeat. Additionally, any subject who requires renal replacement therapy should also be discontinued from drug.
  - e. Hemoglobin <10 mg/dL or hematocrit <30%; platelets <100,000/ $\mu$ L; WBC <4 x  $10^3$ /uL.
  - f. If troponin and CK-MB exceed the 99th percentile of the upper reference limit of the particular assay, serial labs should be obtained along with serial 12-lead ECGs, and cardiology should be consulted. If a patient has symptoms of dyspnea, edema, or a presumptive diagnosis of heart failure, NT-proBNP should be measured as close to the event as possible.
- 3 The criteria for discontinuing or temporarily interrupting study drug with close monitoring are as follows:
  - a. When baseline measure (BLM) are <2x ULN, discontinue if ALT or AST increases >5x BLM.
  - b. When the BLM ≥2X ULN but <5X ULN, discontinue if ALT or AST increases >3X BLM.
  - c. When BLM ≥5X ULN, discontinue if ALT or AST increases >2X BLM.
  - d. For ALT or AST increase >2X BLM accompanied by a concomitant total bilirubin increase to >2X BLM OR an INR increase by >0.2.

Confidential Page 9 of 80

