- 16. Evidence of Acute cellular rejection (ACR) or chronic rejection (CR) or alternative etiologies to NAFLD must be ruled out within 4-6 weeks prior to enrollment into the study by either a liver biopsy or at the discretion (clinical judgement and according to local standard of care) of the treating hepatologist.
- 17. Any of the following laboratory values:

CONFIDENTIAL
PAGE 31 OF 80

- a. White blood cell count < 2.5 x 10^3/uL
- b. Neutrophil count  $< 1.5 \times 10^3 / \text{uL}$
- c. Serum bilirubin > 1.5 mg/dL
- d. Serum ALT >3X ULN
- e. INR >1.2
- f. Renal impairment as demonstrated by baseline estimated glomerular filtration rate (eGFR) <60 mL/min/1.73m^2
- g. Abnormal screening total creatine kinase
- h. Abnormal screening lipase or amylase
- 18. Poorly controlled diabetes as defined by an HbA1c >8.5% within the past 6 months.
- 19. Subjects with history of excessive alcohol intake, defined by ≥21 units of alcohol per week in males and ≥14 units of alcohol per week in females for two years prior to enrollment, where a "unit" of alcohol is equivalent to a 12 ounce (oz.) beer, 4-oz. glass of wine, or 1-oz. shot of hard liquor.
- 20. Subject tests positive for a urine drug screen.
- 21. Subject has a history of chronic (uncontrolled) pain.

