### 5.9.1 Discontinuation of Patients from the Study Drug

- Discontinue patient with an AE of CTCAE grade 3 or higher that is possibly or probably related to IP and discontinue patient with an AE of CTCAE grade 4 regardless of attribution to IP.
- 2 If any of the following criteria are met, the patient must be immediately discontinued from IP and followed until resolution of adverse events and laboratory values return to baseline/stable:
  - a. Total Bilirubin ≥3.0 mg/dL.
  - b. Total CK >5 X ULN.
  - c. Amylase or lipase >ULN.
  - d. eGFR <60 mL/min/1.73 m^2 and where the value is reconfirmed after 24 hours repeat. Additionally, any subject who requires renal replacement therapy should also be discontinued from IP.
  - e. Hemoglobin <10 mg/dL or hematocrit <30%; platelets <100,000/ $\mu$ L; WBC <4 x  $10^3/u$ L.
  - f. If troponin and CK-MB exceed the 99th percentile of the upper reference limit of the particular assay, serial labs should be obtained along with serial 12-lead ECGs, and cardiology should be consulted. If a patient has symptoms of dyspnea, edema, or a presumptive diagnosis of heart failure, NT-proBNP should be measured as close to the event as possible.
- 3 The criteria for discontinuing or temporarily interrupting study drug with close monitoring are as follows:
  - a. When the baseline measurements (BLM) are <2x ULN, discontinue if ALT or AST increases to >5x BLM.
  - b. When the BLM ≥2X ULN but <5X ULN, discontinue if ALT or AST increases to >3X BLM.
  - c. When BLM  $\geq$ 5X ULN, discontinue if ALT or AST increases to  $\geq$ 2X BLM.
  - d. For ALT or AST increases to >2X BLM accompanied by a concomitant total bilirubin increase to >2X BLM OR an INR increase by >0.2.

PAGE 39 OF 80

- e. For elevations of liver enzymes accompanied by symptoms consistent with hepatic injury [e.g., fatigue, nausea, vomiting, right upper quadrant pain or tenderness, fever, rash, and/or eosinophilia (>5%)].
- f. Temporarily interrupted treatment should be permanently discontinued for recurrence of laboratory abnormalities or symptoms following re-challenge.
- g. If a patient lives in a remote area, testing can be performed locally and the results communicated to the PI/site promptly.

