#### 7.4 PROTOCOL DEVIATION

For the purpose of this study, no distinction will be made between Protocol Violations and Deviations. Deviations will be categorized as Clinical Study Report (CSR) non-reportable protocol deviations and as CSR reportable protocol deviations. A CSR non-reportable protocol deviation includes any deviations that do not necessarily influence the results/outcome of primary endpoints or patient safety. A CSR non-reportable protocol deviation does not require immediate notification to the IEC/IRB, unless otherwise specified by IEC/IRB requirements. All CSR non-reportable protocol deviations will be noted in monitoring reports and provided to the PI by monitor.

A CSR reportable protocol deviation includes any violation that may influence the results/outcome of primary endpoints or patient safety. CSR reportable protocol deviations must be reported immediately to the IEC/IRB, as specified by the IEC/IRB requirements. All CSR reportable protocol deviations will also be reported to the Sponsor immediately. These deviations will also be noted in the monitoring reports and provided to the PI by monitor.

Note: Persistent non-compliance of CSR non-reportable protocol deviations may rise to the level of being considered CSR reportable protocol deviations (i.e., persistent non-compliance with dosing).

The Sponsor reserves the right to terminate the study at a given site in the event of monitoring and/or auditing findings of serious or persistent non-compliance with the protocol, SOPs, GCP, and/or applicable regulatory requirement(s) by the PI/institution. In all cases of site closure due to protocol deviations, the IEC/IRB and regulatory authorities will be informed.

The CSR will provide the list of protocol deviation/violations in a separate section. The result will be analysed for all participants with CSR reportable protocol deviations.

Protocol deviations/violations will include but are not limited to the following:

- Patients that did not meet entry criteria but are enrolled into the study;
- Patients that received the wrong treatment or incorrect dose;
- Patients that received an excluded medication:
- Patients that met the discontinuation criteria but continued in the study;
- Failure to report within specified time lines of the planned visits;

Approved by: Protocol No.: SARO.17.010
[name] [name] Version No.: 7.0

CONFIDENTIAL PAGE 57 OF 80

- Failure to perform a study procedure/assessment;

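### Protocol 4.3 admits patients with a WBC of 2.5 to below 4.0 x10^3/uL, but 5.9.1 item 2e stops study drug at any WBC below 4, with no baseline comparison or repeat

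*Protocol*

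**What the plan says.** **Entry.** Protocol 4.3 item 17a excludes "White blood cell count < 2.5 x 10 3 /uL", and the summary's exclusion list gives the same limit. Item 17b adds a neutrophil floor of 1.5 x10^3/uL. Item 17 sets no limit for hemoglobin, hematocrit or platelets.

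**Stop.** Protocol 5.9.1 item 2 opens with the consequence: if any listed criterion is met, "the patient must be immediately discontinued from IP and followed until resolution of adverse events and laboratory values return to baseline/stable". The summary is equally firm: "the patient shall be immediately discontinued from drug and followed until resolution of adverse events". Item 2e lists hemoglobin below 10, hematocrit below 30%, platelets below 100,000/uL and WBC below 4 x10^3/uL. All four are absolute values.

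**Conditions attached to other stops.** The eGFR stop in item 2d applies only where a low value is found "and where the value is reconfirmed after 24 hours repeat". The transaminase stops in item 3 are multiples of the patient's own baseline, for example "discontinue if ALT or AST increases to >5x BLM". Item 2e has neither kind of condition.

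**Deviations.** Protocol 7.4 lists "Patients that met the discontinuation criteria but continued in the study" among the protocol deviations, and the summary has a matching entry.

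**The concern.** An entry limit and a stopping limit for the same analyte should fit together: a patient judged fit to start should not already meet the rule for stopping. For WBC they do not fit. Between 2.5 and 4.0 x10^3/uL the plan enrolls the patient and then calls for study drug to be withdrawn, whether or not the drug has done anything.

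Safety is the primary endpoint and only 15 patients are planned, so two things are at stake. One is drug exposure, the basis of the safety assessment. The other is the meaning of a discontinuation: one triggered by an unchanged count reflects the entry criteria, not tolerability.

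There is a possible further loss. If the patient also leaves the study, Protocol 7.2 calls for Visit 9 procedures, and the Visit 9 list has no MRI. MRI is scheduled only at screening and Week 24, and SAP 6.8 does not carry baseline forward, so that patient's change in MRI-PDFF would be missing.

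**Working it through.** The plan gives no figure of its own here (Protocol 8.4 and SAP 4 report no formal sample-size calculation). The check compares thresholds and then sizes a single event.

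**1. Overlap of the two WBC rules.** Eligible if WBC >= 2.5; stop if WBC < 4.0 (x10^3/uL).

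| WBC | Entry (17a) | Item 2e |
|---|---|---|
| 2.4 | excluded | stop |
| 2.5 | eligible | stop |
| 3.0 | eligible | stop |
| 3.5 | eligible | stop |
| 3.9 | eligible | stop |
| 4.0 | eligible | no stop |
| 4.5 | eligible | no stop |

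The overlap is 2.5 <= WBC < 4.0, a width of 4.0 - 2.5 = 1.5. Item 17b does not close it, since a WBC in this band is compatible with neutrophils of 1.5 or more. The SAP changes neither limit.

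**2. Other analytes in item 2.**

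| Analyte | Excluded at entry (item 17) | Stop (item 2) | Entry against stop |
|---|---|---|---|
| Bilirubin | >1.5 mg/dL | >=3.0 mg/dL | stricter |
| CK | abnormal | >5x ULN | stricter |
| Amylase, lipase | abnormal | >ULN | at least as strict |
| eGFR | <60 | confirmed <60 | at least as strict |
| WBC | <2.5 | <4 | **looser** |
| Hemoglobin | no limit | <10 | **no entry limit** |
| Hematocrit | no limit | <30% | **no entry limit** |
| Platelets | no limit | <100,000/uL | **no entry limit** |

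Counting amylase and lipase as one, five analytes have both limits, and WBC is the only one of the five where entry is looser than the stop. The last three rows have the same weakness in another form: an otherwise eligible patient with stable platelets of 90,000/uL would also meet the stop.

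**3. Size of one such stop.** One patient is 1/15 = 6.7% of the sample. Planned exposure is 15 x 24 = 360 patient-weeks. Assume no restart; item 2 mentions no re-challenge, while item 3f does. The loss is (24 - week of stop)/360.

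| Count acted on at | Weeks lost | Share of 360 |
|---|---|---|
| Day 1 | 24 | 6.7% |
| Week 4 | 20 | 5.6% |
| Week 8 | 16 | 4.4% |
| Week 12 | 12 | 3.3% |

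Week 4 is the first on-treatment laboratory visit in SAP 8.3.5. The protocol leaves laboratory timing to its Table 1, which is not shown, hence the range.

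**4. Frequency.** The documents do not give the share p of eligible patients in the band. As an illustration only, with 15 patients the expected number is 15p and the chance of at least one is 1 - (1 - p)^15.

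| Assumed p | Expected number | Chance of at least one |
|---|---|---|
| 5% | 0.75 | 0.54 |
| 10% | 1.5 | 0.79 |
| 20% | 3.0 | 0.97 |
| 30% | 4.5 | 0.995 |

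These shares are assumptions, and the conclusion does not depend on them.

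**The case against.** The best defense is that item 2e is meant for a fall on treatment. Section 5.9 speaks of laboratory changes from baseline, item 2 ends follow-up once values are back at baseline or stable, and section 6.2.10 provides for repeat tests when medically indicated. A sensible investigator might therefore leave a patient with a stable 3.5 on drug. This is a fair guess at intent, but item 2e does not say it. Within item 2, baseline appears only as the target for follow-up after the stop, and 6.2.10 does not make the stop wait for a repeat.

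A second defense is that a strict stop is prudent in immunosuppressed patients. That stands as a reason for choosing 4. It does not explain admitting patients down to 2.5.

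Three stronger readings are tempting and go beyond the documents:

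- *The investigator has no way round the rule.* The listed deviation concerns patients who continued in the study, while 5.9.1 governs stopping the drug and 4.4 treats withdrawal separately. Keeping the patient on drug would plausibly be a deviation, but that is an inference.
- *WBC is the only mismatch.* This is true only among analytes that have both limits. Hemoglobin, hematocrit and platelets are also exposed.
- *The safety results would be distorted.* The rule errs towards withholding drug. The stopped patient stays in the safety population (SAP 3.2) and normally in the mITT population (SAP 3.1). The listings would show the low baseline count, and the treatment-emergent definition in SAP 8.3.2 should exclude a count that has not worsened.

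It also stands that the per-stop arithmetic would apply to any early stop at the same visit. It does not show that this rule will be triggered.

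**Conclusion.** The conflict holds as written, in both the protocol body and its summary. An eligible patient with an unchanged WBC of 2.5 to below 4.0 x10^3/uL meets a mandatory stop at the first count acted on. The same can happen with hemoglobin, hematocrit or platelets.

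Confidence is high on the text and much lower on the practical effect. One such stop costs about 20 of 360 patient-weeks (range 12 to 24), assuming that it is not reversed and depending on when the count is acted on. How often it would happen cannot be estimated from the documents. It merits correction because following the rule gives the wrong action for an eligible patient and the remedy is cheap. It does not threaten the trial's validity.

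**What to change.** Amend both copies (Protocol 4.3 item 17 with 5.9.1 item 2e, and the summary) in one of two ways:

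- **Match entry to the stop.** Raise the WBC entry limit to equal the stopping limit, and add entry limits for hemoglobin, hematocrit and platelets that match item 2e.
- **Condition the stop.** For patients who enter below a 2e limit, stop on a fall from baseline confirmed by a repeat, with an absolute safety floor set by the sponsor and investigator. The 24-hour repeat in item 2d and the baseline multiples in item 3 are ready models.

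Neither adds patients. The first narrows eligibility to a degree the documents do not allow one to estimate. The second costs one repeat count and makes the stop less conservative in immunosuppressed patients. If 17a stays at 2.5, a WBC floor that no eligible patient already meets can be no higher than 2.5, so the unconditional stop for those patients drops from 4.0 to 2.5 or lower. That is a real safety trade-off and should be decided openly.

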**Table 3: Safety Laboratory Assessments** 

Hematology	Hematocrit, hemoglobin, MCHC, MCV, platelet count, MPV, RBC count, WBC count, differential WBC count
	Coagulation Panel: APTT, PT/INR ratio, TT.

Approved by:	Protocol No.: SARO.17.010
[name] [name]	Version No.: 7.0

CONFIDENTIAL
PAGE 44 OF 80

_, ,	O/ 11 (0 1 1 1 1 0 1 0		
	Liver function tests: AST, ALT, ALP, total bilirubin (with Conjugated		
	bilirubin), GGT, total protein and albumin		
	Amylase and lipase		
	Renal function tests: BUN, serum creatinine, eGFR		
	eGFR will be calculated by using Chronic Ki		
	Epidemiology Collaboration (CKD-EPI) equa		
	Creatine phosphokinase, CK-MB, troponin 1 and NT		
	Serum electrolytes: sodium, potassium, calcium, bica		
	Gut hormones: Ghrelin, glucagon like peptide, leptin,	resistin, and	
	adiponectin		
	HbA1c and fasting plasma glucose		
8.	HIV type 1 and type 2 HAV IgM,		
	HBsAg		
HCV Immunosuppression level (tacrolimus, cyclosporine or			
		sirolimus)	
	CMV (IgG), and EBV VCAIgG		
•	Physical examination (appearance, color, specific gravity and pH); microscopy (epithelial cells, red blood cells, pus or white blood cells, casts and crystals) and chemical examination (protein, glucose, bilirubin, urobilinogen, ketone bodies, nitrite and blood) Urine drug testing		
	Serum pregnancy test for women of childbearing poter Visit 1, and Visit 8.	ntial at the Screening	
	Urine pregnancy test will be performed on Visit 2 to7	and Visit 9.	

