### 8.4 DETERMINATION OF SAMPLE SIZE

Due to the exploratory nature of this study, no formal power calculations were used to determine sample size. The number of patients was chosen based on clinical experience with other similar proof of concept studies. Approximately 5 patients will be included in the pharmacokinetic assessment sub-study.

Approved by: [name] [name] Protocol No.: SARO.17.010

CONFIDENTIAL
PAGE 62 OF 80

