### 8.3.5 Laboratory Results

Clinical laboratory evaluations consist of hematology, clinical biochemistry and urinalysis. Laboratory assessment for the urinalysis, lipid profiles and HbA1c will be performed at Screening, Baseline, Week 12 and Week 24 visits. Laboratory assessments for FSIVGTT and metabolic flexibility assessments will be conducted at Baseline and Week 24 Visits. Laboratory assessments for all other parameters will be performed at screening, baseline and Week 4, 8, 12, 16, 20, 24 and 28 visits. Laboratory values will be presented using the International System of Units (SI units).

Observed and changes from baseline values will be summarized descriptively (N, mean, median, standard deviation, minimum, and maximum values) for all hematology and biochemistry parameters at each assessment. A summary table of the categorical grade shift changes using the normal ranges from baseline to last study visit will be provided.

For summary purposes, laboratory values that are listed as above or below particular thresholds will be numerically listed as above or below that threshold, respectively, by the minimum measured amount for that parameter. For example, if a parameter is measured to

Document Title:	Statistical Analysis Plan		
Version Number:	1.0	Date:	31 Dec 2021
Protocol Number:	SARO.17.010	Sponsor Name:	Zydus Therapeutics Inc.

A listing will be provided which contains data for each laboratory parameter for all enrolled patients.

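### The haemoglobin stop limit is printed in mg/dL, 1000 times too low, so only the hematocrit limb of item 2e can detect anaemia

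*Protocol*

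**What the plan says.** Protocol section 5.9.1 lists laboratory limits under a mandatory rule: "If any of the following criteria are met, the patient must be immediately discontinued from IP". Item 2e of that list begins "Hemoglobin <10 mg/dL or hematocrit <30", where the last figure is a percentage, and goes on to platelet and white-cell limits. The synopsis gives the same haemoglobin limit in the same unit under its heading on discontinuation from study drug. Neither document restates the limit in another unit, and the SAP does not restate the drug-stop limits at all.

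Three other provisions bear on the point.

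- Protocol section 7.4 counts as a deviation "Patients that met the discontinuation criteria but continued in the study", and the synopsis has an equivalent entry.
- Haemoglobin, hematocrit and MCHC are all in the haematology panel (protocol Table 3).
- Item 1 of section 5.9.1 is a separate stop based on CTCAE grade: "Discontinue patient with an AE of CTCAE grade 3 or higher that is possibly or probably related to IP". It also stops drug for any grade 4 event whatever the attribution.

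**The concern.** A haemoglobin limit in mg/dL sits beside a hematocrit limit of 30%. The two should describe roughly the same degree of anaemia, and they do not. Read literally, one of the two anaemia triggers in a mandatory safety rule is inert.

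The patients affected are those with a hematocrit of 30% or more and a haemoglobin below the limit presumably intended. Under the printed rule such a patient may stay on drug and commits no deviation. Under the g/dL reading the same patient must stop, and continuing is a listed deviation. Section 7.4 requires deviations that may influence patient safety to go to the ethics committee and the sponsor immediately, so the two readings lead to different actions.

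This is also the only numeric haemoglobin limit in the protocol. Exclusion criterion 17 sets laboratory limits at entry but none for haemoglobin or hematocrit. Safety is the primary endpoint.

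**Working it through.** **Inputs from the documents.** Haemoglobin (Hb) limit 10 mg/dL and hematocrit (Hct) limit 30%, joined by *or* (protocol synopsis and section 5.9.1, item 2e). Planned enrolment 15 (protocol section 4.1).

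**Assumptions from outside the documents.** The intended unit is g/dL. MCHC, for which the documents give no values, lies between 30 and 36 g/dL.

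**Step 1: convert the printed limit.** 10 mg/dL ÷ 1000 = 0.010 g/dL. Multiplied by 10, this is 0.1 g/L.

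**Step 2: compare the two limbs.** By definition Hb = Hct × MCHC, so the MCHC implied by a pair of limits is Hb ÷ Hct.

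- As printed: 0.010 ÷ 0.30 = 0.033 g/dL.
- Read as 10 g/dL: 10 ÷ 0.30 = 33.3 g/dL.
- Ratio: 33.3 ÷ 0.033, which is 1000 before rounding.

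The same check in the other direction uses Hct = Hb ÷ MCHC over MCHC 30 to 36.

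- As printed: 0.010 ÷ 30 = 0.033% down to 0.010 ÷ 36 = 0.028%.
- Read as 10 g/dL: 10 ÷ 30 = 33.3% down to 10 ÷ 36 = 27.8%, which brackets the printed 30%.

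The limbs therefore agree in g/dL and disagree 1000-fold as printed.

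**Step 3: who escapes item 2e under the literal reading.** The hematocrit limb fires when Hb < 0.30 × MCHC. The missed band runs from that value up to, but not including, 10 g/dL. Its width is max(0, 10 − 0.30 × MCHC). The last column takes a patient with Hb 9.5 g/dL, whose Hct is 9.5 ÷ MCHC.

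| MCHC (g/dL, assumed) | Hb at Hct 30% (g/dL) | Missed band (g/dL) | Width (g/dL) | Hct at Hb 9.5 g/dL |
|---|---|---|---|---|
| 30 | 9.0 | 9.0 to 10 | 1.0 | 31.7%, missed |
| 31 | 9.3 | 9.3 to 10 | 0.7 | 30.6%, missed |
| 32 | 9.6 | 9.6 to 10 | 0.4 | 29.7%, stopped |
| 33 | 9.9 | 9.9 to 10 | 0.1 | 28.8%, stopped |
| 33.3 | 10.0 | none | 0 | 28.5%, stopped |
| 34 | 10.2 | none | 0 | 27.9%, stopped |
| 36 | 10.8 | none | 0 | 26.4%, stopped |

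**Step 4: scale.** One patient classified differently would be 1 ÷ 15 = 6.7% of planned enrolment. This shows what one patient amounts to. It does not estimate how many fall in the band, and the documents give no basis for such an estimate.

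**Step 5: reach into the analysis.** The study has no power calculation (protocol section 8.4). The safety analysis is descriptive, and the laboratory shift tables in SAP section 8.3.5 use normal ranges rather than this limit. The limit affects reporting only through who is recorded as having met a discontinuation criterion.

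**The case against.** The strongest reply is that this is an obvious slip of the pen. A limit of 0.01 g/dL is impossible, the hematocrit limit on the same line points to g/dL, and a clinician would very probably read it that way. Nothing in the documents suggests that the site or sponsor would apply the literal figure.

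Even if they did, the hematocrit limb catches nearly the same patients. The band is widest only at the lowest MCHC assumed, and those values come from outside the documents.

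Other safeguards also remain. These are the CTCAE-based stop in item 1, investigator review of every laboratory report (protocol section 7.1), reporting and follow-up of clinically significant abnormal values as adverse events (section 9.4.1), and regular review of safety data by the monitoring committee (section 7.5).

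Most of this stands, and it keeps the point small. It does not make the line correct. A mandatory stopping rule should work as printed, without staff silently correcting its unit. Nor does item 1 replace the laboratory trigger: it needs an adverse event graded 3 or higher and judged possibly or probably related, or one of grade 4, whereas item 2e applies to the laboratory value itself whatever its cause. Investigator review leaves the action to judgement. The same unit appears in both the synopsis and section 5.9.1, so a fault in reading the PDF is unlikely.

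**Conclusion.** The concern holds and is minor. The printed haemoglobin limit is too low by a factor of 1000 and cannot be met, which leaves the hematocrit limit as the only working anaemia trigger within item 2e. It is not the trial's only safeguard against anaemia.

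In practice, the gap is confined to patients with low MCHC and a haemoglobin somewhat below 10 g/dL. With 15 patients it may contain nobody. The factor of 1000 is a plain unit conversion. The width of the gap rests on two assumptions: that g/dL was intended, and that MCHC takes the values in the table. No sample size, estimate or planned summary changes.

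**What to change.** Change mg/dL to g/dL for haemoglobin in the synopsis and in section 5.9.1, item 2e, once the sponsor's medical expert has confirmed the unit. Use the corrected limit when deciding which patients met the discontinuation criteria but continued.

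If dosing has already finished, a documented clarification serves the same purpose, provided it is in place before deviations are finalised. SAP section 1 requires deviations to be identified before statistical analysis starts.

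The cost is one unit corrected in two places at the next amendment, with no added patients, visits, tests or analyses.
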